^c A follow-up phone call will take place on Day 6 ± 1 of the final treatment period, to ensure the ongoing wellbeing of the subjects. If a subject reports any AEs that present a cause for concern, they will be required to attend the clinical unit for a (unscheduled) follow-up visit. Assessments may be performed at the unscheduled follow-up visit as indicated

^d Update only

^e Weight only

^f Period 1 only

^g Subjects will be randomised immediately prior to dosing in Period 1, for allocation of regimens across Periods 1 and 2

^h Targeted (symptom driven) physical examination of the relevant body system(s) as clinically indicated, as per the Investigator's judgement

ⁱ Periods 2 to 4 only

^j Haematology and clinical chemistry at each time point including virology and FSH (post-menopausal female subjects only) at screening

^k All female subjects

^l Blood pressure, heart rate, oral temperature and respiratory rate will be measured at each time point

^m The taste/palatability questionnaire will be started within 10 minutes of each delafloxacin Powder for Oral Suspension (i.e., test) regimen administration. See [Appendix 3](#) for details of the taste/palatability questionnaire

Appendix 3 Example Taste/Palatability Questionnaire**QSC300553 (ML-DEL-101-3727-1) Taste Questionnaire**Study Period: Regimen: Subject Number: Subject Initials: Start time:

(to be started within 10 minutes of dosing)

Date: **Question 1**

All aspects considered (smell, sweetness, bitterness, flavour, mouthfeel/texture, grittiness, and aftertaste), how would you rate your overall liking of this product:

NOTE: Tick 1 box below in blue or black pen

Dislike extremely	Dislike very much	Dislike moderately	Dislike slightly	Neither like nor dislike	Like slightly	Like moderately	Like very much	Like extremely
								

Question 2

We want to know how much you like certain aspects of the product: smell, sweetness, bitterness, flavour, mouthfeel/texture, grittiness, and aftertaste. Please rate each test product independently of any previous taste questionnaires. **NOTE: Tick 1 box in the row for each aspect**

	Dislike extremely	Dislike very much	Dislike moderately	Dislike slightly	Neither like nor dislike	Like slightly	Like moderately	Like very much	Like extremely	Not detectable
Smell										
Sweetness										
Bitterness										
Flavour										

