- If there are other events (i.e., same SOC and PT code) with a maximum severity recorded as “mild” for that subject and regimen, then the maximum observed severity for that subject will be categorised and presented as “missing”

When summaries are presented by relationship to regimen, “missing” will be handled as follows:

- If there are other events (i.e., same SOC and PT code) with a most closely related association recorded as “possibly related” or “related” for that subject and regimen, then the maximum observed relationship for that subject will be categorised and presented as “possibly related” or “related”, respectively.
- If there are other events (i.e., same SOC and PT code) with a most closely related association recorded as “unrelated” for that subject and regimen, then the maximum observed relationship for that subject will be categorised and presented as “missing”.

Where the start date of an AE is missing and the stop date is on or after the day of first administration of test-product, or both the start and stop dates are missing, then a “worst-case” scenario will be assumed i.e., the AE is assumed to have occurred post-administration and is therefore considered treatment-emergent. If a partial start date/time is available, then the event will be considered as treatment-emergent, unless the partial information suggests otherwise.

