11.3.1 Summary Tables for Adverse Events

All pre-dose AEs (as defined in [Section 11.3](#)) will be excluded from the summary tables, but will be listed.

Descriptive statistical methods will be used to summarise the TEAE data.

The number and percentage of subjects reporting each TEAE will be presented for both SOC and PT. For summaries by SOC and PT, with the exception of TEAEs by severity and relationship to IMP, the number of subjects, and the number of events will be summarised. For summaries by severity and relationship, only the number of subjects will be summarised.

For counts of subjects experiencing events the following will apply:

- A subject experiencing TEAEs in more than one body system, within a study period, will be counted once in the total number of subjects with TEAEs in that study period
- A subject with more than 1 TEAE in the same SOC, within a study period, counts only once at the SOC level
- A subject with more than 1 TEAE in the same PT, within a study period, counts only once at the PT level

For TEAE event counts, all events are included.

When it is necessary to calculate percentages, the denominator will be the total number of subjects in the safety analysis set for that regimen or study period and the numerator will be the total number of subjects reporting a TEAE within the relevant category.

Summaries presented for SOC and PT will be presented in descending order of frequency overall i.e. most frequently reported SOC in the study and then by most frequently reported PT in the study within each SOC.

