11.3.1.1 Overall Summary of Adverse Events

The following will be summarised by regimen and overall for the safety analysis set:

- Number and percentage of subjects reporting TEAEs
- Number and percentage of subjects reporting severe TEAEs
- Number and percentage of subjects reporting ADRs
- Number and percentage of subjects reporting serious TEAEs
- Number and percentage of subjects reporting TEAEs leading to subject withdrawal
- Number and percentage of subjects reporting TEAEs leading to death
- Total number of TEAEs
- Total number of severe TEAEs
- Total number of IMP-related ADRs

- Total number of serious TEAEs
- Total number of TEAEs leading to subject withdrawal
- Total number of TEAEs leading to death

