If the start date/time of an AE record is missing or incomplete, preventing a clear allocation of the AE to a single treatment period, a worst-case consideration (see below) will be done aiming to allocate the AE record to one single treatment period, if possible. When a worst-case consideration is needed, any available start or end date/time will be considered in assignment of the AE to a treatment period.

- An AE which according to the available information of its start date/time could belong to screening as well as to the first treatment period will only be placed in the first treatment period
- An AE which according to the available information of its start date/time could belong to two (or more) subsequent treatment periods will be allocated to all the matching treatment periods (i.e., these AE records will be replicated and reported once in each of these matching treatment periods where IMP was administered before the end date)
- An AE which according to the available information of its start date/time could belong to all possible treatment periods will be allocated to all the treatment periods

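### Replicated adverse events with an unclear start date are not de-duplicated in the Overall event totals, and the missing-start rule in SAP 11.3 uses a different anchor from the TEAE definition

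*SAP*

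**What the plan says.** **Allocation to periods.** SAP 14.1 covers AEs whose start is missing or too incomplete to identify one period. It aims for a single period where possible, and "any available start or end date/time will be considered in assignment of the AE to a treatment period". Three rules follow:

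- An event that "could belong to screening as well as to the first treatment period will only be placed in the first treatment period".
- For an event that fits two or more later periods, "these AE records will be replicated and reported once in each of these matching treatment periods where IMP was administered before the end date".
- An event that "could belong to all possible treatment periods will be allocated to all the treatment periods".

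**Counting.** SAP 11.3.1 states: "For TEAE event counts, all events are included". SAP 11.3.1.1 introduces its list of subject counts and event totals with "The following will be summarised by regimen and overall for the safety analysis set". The list includes total TEAEs, severe TEAEs, ADRs, serious TEAEs, and TEAEs leading to withdrawal or death. Mock Tables 14.3.1 and 14.3.2 have an Overall column with an event count, E. SAP 11.3.1.2 counts a subject only once overall. No section says how copied records enter the Overall event count.

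**Treatment-emergent status.** SAP 11.3 defines TEAEs from the first dose of IMP. Its fallback for missing dates has a different anchor. It applies "Where the start date of an AE is missing and the stop date is on or after the day of first administration of test-product", or when both dates are missing. A partial start date has its own sentence, which makes the event treatment-emergent by default and does not mention *test-product*.

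**Meaning of *test*.** SAP 9.1.1, 9.1.3 and 9.6 use *test* for the powder, and *reference* for the tablet. The schedule of assessments has the same usage: "delafloxacin Powder for Oral Suspension (i.e., test) regimen administration".

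**The concern.** There are two separate problems, both in how AEs without a usable start date are handled.

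First, showing one event under every regimen that might have caused it is a reasonable worst case for the regimen columns. The Overall column does not attribute the event to any regimen, so counting it several times there only inflates the total. The planned quality control may not catch this. SAP 14.2.1 checks the AE tables against the listing, and Listing 16.2.7.2 is laid out by period, so the copies could appear in both and agree.

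Second, in sequence AB the first powder dose is in Period 2. Read literally, the 11.3 fallback does not apply to an undated event that ended after the tablet dose but before the powder dose. SAP 14.1 would place the same event in Period 1. A programmer who took failure of the 11.3 rule to mean pre-dose would leave the event out of the summary tables (11.3.1) and class it as unrelated (11.3). Only the tablet could be affected.

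Safety and tolerability is a secondary objective. With 16 planned subjects the event counts may be small, so a single extra record could be visible.

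**Working it through.** The documents give no AE count or rate of undated AEs, so there is no stated figure to reproduce. The check applies the rules to an AE with no start date at all.

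**Inputs**

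- Periods: 3, or 4 if optional Period 4 runs (Protocol 8.1).
- Minimum intervals between doses: 4 days from Period 1 to 2, then 14 days each (Protocol 8.1). Taken dose to dose, doses fall on Days 1, 1 + 4 = 5, 5 + 14 = 19 and 19 + 14 = 33.
- Allocation: 8 subjects AB and 8 BA (SAP 5.4).
- First IMP dose: Day 1 in both sequences. First powder dose: Day 5 in AB, Day 1 in BA.

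**Step 1: copies in the Overall event count.** Copies = number of periods dosed by the stop date, or all periods if the stop date is missing too.

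| Stop date | Copies, Period 4 run | Copies, Period 4 not run |
|---|---|---|
| Days 1–4 | 1 | 1 |
| Days 5–18 | 2 | 2 |
| Day 19 to before any Period 4 dose | 3 | 3 |
| After the Period 4 dose | 4 | not applicable |
| Missing | 4 | 3 |

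One true event with both dates missing therefore gives Overall E = 4 or 3. The Overall subject count stays at 1. Each regimen column gains one subject, 1/16 = 6.25%, which is the intended worst case.

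The relative effect depends on the total. Taking assumed true totals that include one such event:

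| True TEAEs | Overall E with Period 4 (+3) | Overall E without (+2) |
|---|---|---|
| 5 | 8 (+60%) | 7 (+40%) |
| 10 | 13 (+30%) | 12 (+20%) |
| 20 | 23 (+15%) | 22 (+10%) |

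With 0, 1 or 2 such events in the study (an assumption), the excess is 0, 3 or 6 with Period 4, and 0, 2 or 4 without.

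**Step 2: the two anchors for treatment-emergent status.** The fallback applies if the stop date is on or after the anchor day, or if the stop date is missing.

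| Sequence | Stop date | Applies with *test-product* anchor | Applies with IMP anchor | Periods under 14.1 |
|---|---|---|---|---|
| AB | before Day 1 | no | no | none |
| AB | Days 1–4 | **no** | **yes** | Period 1 (tablet) |
| AB | Day 5 or later | yes | yes | 2 or more |
| AB | missing | yes | yes | all |
| BA | before Day 1 | no | no | none |
| BA | Day 1 or later, or missing | yes | yes | as in Step 1 |

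The anchors disagree in one row only. In that row 14.1 still puts the event in Period 1, so the SAP contains two incompatible instructions.

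**The case against.** **Replication is declared.** A reader might infer that 14.1 contradicts itself, because it aims for one period and then copies into several. It does not. The aim is qualified, and replication is the stated fallback when the dates cannot settle the matter. Nor does it override the rule in 11.3 that assigns a TEAE to the regimen of first occurrence, since that rule needs a known onset. This part of the objection stands, and replication by regimen should stay. It does not justify multiple counting in the Overall column.

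**The multiplication is an extreme case.** Four copies need Period 4 to run and no date information that narrows the range. Three also need a long window of uncertainty. Onset date and time are recorded for every AE (Protocol 14.3), and queries are raised and resolved (Protocol 15.2). A serious event is reported within 24 hours (Protocol 16.3.1), so an undatable serious event is remote. This stands as a limit on likelihood. Safety summaries are also descriptive, so no formal comparison is biased.

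**A reader might infer that the SAP drops tablet-period events in sequence AB and so undercounts the tablet.** The documents do not support that. Events with a full start date, a partial start date, or neither date are handled the same under both anchors. In the one remaining case, 11.3 fails to apply its worst-case assumption but does not call the event pre-dose, and 14.1 places it in Period 1. The window also falls while subjects stay in the unit between Periods 1 and 2 (Protocol 8.1). The intervals at home, where undated events are likelier, come after Period 2, when subjects in both sequences should already have had the powder.

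**The term *test-product* may be loose wording for IMP.** Protocol 11.2 has a heading on test preparations that covers the tablet as well. This is plausible, but it is a protocol heading. The SAP's own usage separates test from reference, including in 6.2, so the literal reading is open to a programmer.

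**Conclusion.** Both points hold as wording defects with a small expected effect.

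- **Overall event totals.** As written, one AE with an unclear start can count up to 3 times in Overall E, or 4 times if Period 4 runs. The inflation is confined to event totals. Overall subject counts and percentages are right, and the regimen columns show a declared worst case.
- **Anchor.** The *test-product* wording conflicts with the TEAE definition in 11.3 and with the allocation in 14.1. It matters only for AB events with no start date and a stop date from the tablet dose to before the Period 2 dose (Days 1–4 at the minimum washout). The 8 AB subjects are those who could be affected, not those expected to be. Handling is contradictory, but loss of events is not established.

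This rests on the assumption that undated AEs are rare: 0 to 2 in the whole study, and about none in the AB window. The documents give no rate. The conclusion also takes the rules literally, since no further counting convention is stated. The priority is low: worth correcting because it is nearly free, with no bearing on the pharmacokinetic conclusions.

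**What to change.** 1. In SAP 11.3, replace *test-product* with *IMP* in the missing-start rule. It then agrees with the TEAE definition and with 14.1, and the AB case becomes a TEAE under the tablet. BA subjects do not change.
2. In SAP 14.1 and 11.3.1, add: *An AE replicated under the worst-case rule is shown in each matching regimen column but is counted once in the Overall column and in all overall event totals.*
3. Identify copies by subject and AE number, which Listing 16.2.7.2 already carries. An AE that worsens in a later period is a new AE under 11.3 and should keep its own number, so that the key does not merge it.
4. Footnote the affected tables with the number of replicated AEs, so that a reader can see why the regimen columns may add to more than the Overall count.

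The cost is a few sentences in the SAP, one de-duplication key and one footnote. Data collection, the analysis sets and the pharmacokinetic analysis are unchanged.

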14.2 Quality Control of Summary Tables, Figures and Listings and Statistical Analysis

Isolated data errors detected as a result of the QC checks that are deemed significant (i.e., errors that would impact the interpretation of the results in relation to the study objectives) will be corrected as per the data management plan. Systematic data errors will be investigated further. The data will be corrected if necessary, and the appropriate table, figure, and/or listing re-generated and then re-checked.

In addition to QC checks, a documented peer review will be performed of all SAS Software-generated report standard TFLs, including a review of SAS Software code and program log files.

14.2.1 Quality Control - Summary Tables

Manual QC methods (i.e., comparison of results in the table to results calculated by a calculator or spreadsheet) will be used for all analyses and summary tables. All summary tables will be QC'd as follows:

- Where tables are presented by regimen (i.e., no time points), QC will alternate between regimen to avoid the same regimen being QC'd every time. For tables presented by regimen only (i.e., no time points), all summary statistics for 1 regimen will be QC'd
- Where tables are presented by regimen and time point, QC will alternate between regimen and time point, to avoid the same regimen being QC'd every time
- For tables presented by regimen and time point, a single regimen at 1 time point in each table will be QC'd
- Where tables are produced using a macro for multiple parameters, a minimum of 3 tables, using different regimens or combinations of regimens and time point as appropriate, will be QC'd
- For AEs, the treatment details will be 100% QC'd against the randomisation schedule (If applicable) for all subjects
- AE summary tables will be 100% checked using the relevant data listing

14.2.2 Quality Control - Figures

All figures will be QC'd manually using the corresponding/appropriate summary table or data listing, as follows:

- Across all figures, QC will alternate between regimen, to avoid the same regimen being QC'd every time
- Where a figure presents data from more than 1 regimen, only 1 regimen will be QC'd. However, all data points for that regimen will be checked
- Where figures are produced using a macro for individual subjects and/or multiple parameters, a minimum of 3 figures will be QC'd
- Mean figures will be QC'd using the corresponding summary table
- Figures showing individual data will be QC'd using the corresponding data listing

14.2.3 Quality Control - Data Listings

All data listings will be subjected to a 100% manual check against the eCRF study build specifications or other appropriate source data for a minimum of 2 subjects. If appropriate, the subjects checked will include at least 1 subject who withdrew early from the study.

The study treatment allocation details on the dosing data listing will be 100% QC checked against the study randomisation schedule.

14.2.4 Quality Control - Statistical Analysis

QC of statistical analyses will be performed by peer review of program code, log, and output. This will be performed by a statistician at Quotient who is not responsible for performing the statistical analysis.

15 SAS Data Transfer

All study data used for analysis and reporting will be transferred to Melinta on issue of the final CSR. Datasets will be provided in SAS transport file format (XPT). Each dataset will be an individual transport file and will be performed in compliance with ADaM (IG v1.1). This will include define.xml (v2.0) output as well as a Data Reviewers Guide (adrg) in PDF format which will be linked to the define.xml. There will be one draft transfer ADaM define.xml and one final, issued on finalisation of the CSR.

Details of the SDTM define.xml are documented in the study Data Management Plan.

16 Programming Conventions

Quotient standards for layout of TFLs and programming conventions will be used as follows:

- Courier new, font size 8
- Landscape
- A4 paper
- US letter size (8.5 x 11)

Tables and listings will be produced as MS Word 2016 (or more recent version) documents and figures will be produced as PDF files. Listings will be sorted by subject ID and period (where applicable), i.e., all subjects will be presented in sequential order, and then chronologically within each subject where both periods are presented; treatment sequence will be displayed for listings where no period is required to be presented.

The mock tables ([Section 21](#)), figures ([Section 22](#)), and data listings ([Section 23](#)) presented are a representation of Quotient reporting standards. However, these are provided for illustrative purposes only. The numbering and titles, formatting, labelling, footnotes, and cosmetic appearance of all output may be modified or additional labelling/footnotes may need to be added during analysis and reporting, for clarification purposes. Any such changes will not be regarded as changes to planned analyses.

17 Reference List

16.2.4.9	Follicle Stimulating Hormone Individual Values: All Enrolled Post-Menopausal Female Subjects
	Dosing Details and Meal Details
16.2.5.1.1	Dosing Details Individual Values: All Enrolled Subjects
16.2.5.1.2	Meal Details for Fed Dosing Individual Values: All Enrolled Subjects

Listing Number	Listing Title
	Plasma Pharmacokinetic Concentration and Parameters
16.2.5.2	Blood Sample Collection Details for Pharmacokinetic Analysis and Plasma Concentrations: Delafloxacin Individual Values: All Enrolled Subjects
16.2.6.1	Plasma Pharmacokinetic Parameters: Delafloxacin Individual Values: All Enrolled Subjects
	Taste Assessment
16.2.6.2	Taste Assessment Individual Values: All Enrolled Subjects
	Adverse Events
16.2.7.1	Pre-dose Adverse Events Individual Values: All Enrolled Subjects
16.2.7.2	All Treatment-Emergent Adverse Events Individual Values: All Enrolled Subjects
16.2.7.3	Serious Adverse Events Individual Values: All Enrolled Subjects
	Laboratory Data
16.2.8.1	Blood Sample Collection Details for Laboratory Analysis Individual Values: All Enrolled Subjects
16.2.8.2	Haematology Individual Values: All Enrolled Subjects
16.2.8.3	Haematology Individual Values Outside the Reference Range: All Enrolled Subjects
16.2.8.4	Clinical Chemistry Individual Values: All Enrolled Subjects
16.2.8.5	Clinical Chemistry Individual Values Outside the Reference Range: All Enrolled Subjects
16.2.8.6	Urinalysis Sample Collection Individual Values: All Enrolled Subjects
16.2.8.7	Urinalysis Individual Values: All Enrolled Subjects
16.2.8.8	Urinalysis Individual Values Outside the Reference Range: All Enrolled Subjects
	Vital Signs and ECGs
16.2.9.1.1	Vital Signs Individual Values: All Enrolled Subjects
16.2.9.1.2	Vital Signs Individual Values Outside the Reference Range: All Enrolled Subjects

Listing Number	Listing Title
16.2.9.2.1	ECGs Individual Values: All Enrolled Subjects
16.2.9.2.2	ECGs Individual Values Outside the Reference Range: All Enrolled Subjects
	Other Data
16.2.9.3	Physical Examination Data Individual Values: All Enrolled Subjects

21 Mock Tables

TABLE 14.1.1
Subject Disposition by Reason
Summary Statistics: All Enrolled Subjects

	Sequence		
	ABC<D> (N=X)	BAC<D> (N=X)	Overall (N=X)
	n (%)	n (%)	n (%)
Subjects enrolled (1)	xx (xx.x)	xx (xx.x)	xx (xx.x)
Subjects dosed	xx (xx.x)	xx (xx.x)	xx (xx.x)
Subjects completed	xx (xx.x)	xx (xx.x)	xx (xx.x)
Subjects discontinued	xx (xx.x)	xx (xx.x)	xx (xx.x)
Reason for discontinuation			
REASON 1	xx (xx.x)	xx (xx.x)	xx (xx.x)
REASON 2	xx (xx.x)	xx (xx.x)	xx (xx.x)
REASON 3	xx (xx.x)	xx (xx.x)	xx (xx.x)
...
<All categories on source>	xx (xx.x)	xx (xx.x)	xx (xx.x)

Note: Investigational Medicinal Product is delafloxacin, POS = powder for oral suspension, Regimen B, C and D with orange flavour
Regimen Key: A = 450 mg tablet (reference) fasted, B = 450 mg POS fasted, C = xxx mg POS <status>, D = xxx mg POS <status>
(1) An enrolled subjects signed the informed consent, qualified per the inclusion/exclusion criteria and was randomised
A subject may be discontinued for one reason only

PROGRAM PATH: X:\~\QSCXXXXXX\~\TFLS\PRODUCTION\TAB-XX

DDMMYYYY HH:MM

Programming note: This table will be continued for all reasons for discontinuation as recorded
on the source. If none of the subjects discontinued from the study early
then reasons for discontinuation will not be populated in the summary table
Percentages are based on the number of subjects enrolled in the respective sequence

Sponsor/Quotient Sciences Confidential

Melinta Therapeutics
Protocol: ML-DEL-101-3727-1

Page x of y

TABLE 14.1.2.1
Analysis Populations
Summary Statistics: All Enrolled Subjects

	Sequence		
	ABC<D> (N=X) n (%)	BAC<D> (N=X) n (%)	Overall (N=X) n (%)
Subjects in safety population	xx (xx.x)	xx (xx.x)	xx (xx.x)
Reason for exclusion from safety population			
<All categories on source listing>	xx (xx.x)	xx (xx.x)	xx (xx.x)

Subjects in PK population	xx (xx.x)	xx (xx.x)	xx (xx.x)
Reason for exclusion from PK population			
<All categories on source listing>	xx (xx.x)	xx (xx.x)	xx (xx.x)

Subjects in taste/palatability population	xx (xx.x)	xx (xx.x)	xx (xx.x)
Reason for exclusion from taste/palatability population			
<All categories on source listing>	xx (xx.x)	xx (xx.x)	xx (xx.x)

Note: Investigational Medicinal Product is delafloxacin, POS = powder for oral suspension, Regimen B, C and D with orange flavour
Regimen Key: A = 450 mg tablet (reference) fasted, B = 450 mg POS fasted, C = xxxx mg POS <status>, D = xxxx mg POS <status>
A subject may be excluded for more than one reason

PROGRAM PATH: X:\~\QSCXXXXXX\~\TFLS\PRODUCTION\TAB-XX DDMMYYYY HH:MM

Programming note: Percentages are based on the number of subjects enrolled in the respective sequence

Sponsor/Quotient Sciences Confidential

Melinta Therapeutics
Protocol: ML-DEL-101-3727-1

Page x of y

TABLE 14.1.2.2
Safety Analysis Set
Summary Statistics: Safety Population

	450 MG TAB FASTED (N=X) n (%)	450 MG POS FASTED (N=X) n (%)	XXX MG POS <STATUS> (N=X) n (%)	XXX MG POS <STATUS> (N=X) n (%)
Subjects in safety analysis set	xx (xx.x)	xx (xx.x)	xx (xx.x)	xx (xx.x)
Reasons for exclusion from safety analysis set <All categories from source>	xx (xx.x)	xx (xx.x)	xx (xx.x)	xx (xx.x)

Note: Investigational Medicinal Product is delafloxacin, POS = powder for oral suspension, Regimen B, C and D with orange flavour
Regimen Key: A = 450 mg tablet (reference) fasted, B = 450 mg POS fasted, C = xxx mg POS <status>, D = xxx mg POS <status>
A subject may be excluded for more than one reason

PROGRAM PATH: X:\~\QSCXXXXXX\~\TFLS\PRODUCTION\TAB-XX DDMMYYYY HH:MM

Programming note: A similar table will be produced for the PK Analysis Set and Taste/palatability Analysis Set (and Subset[s], if required), i.e. Table [14.1.2.3] and Table [14.1.2.4]
Each analysis set/subset will be a subset of their respective population and percentages will be based on number of subjects in each population

Sponsor/Quotient Sciences Confidential

Melinta Therapeutics
Protocol: ML-DEL-101-3727-1

Page x of y

TABLE 14.1.3
Demographic and Baseline Characteristics
Summary Statistics: Safety Population

	n	Sequence		
		ABC<D> (N=X)	BAC<D> (N=X)	Overall (N=X)
Age (years)	n	xx	xx	xx
	Mean	xx.xx	xx.xx	xx.xx
	SD	xx.xx	xx.xx	xx.xx
	Median	xx.xx	xx.xx	xx.xx
	Min	xx.x	xx.x	xx.x
	Max	xx.x	xx.x	xx.x
Ethnicity n(%)	<All categories on source>	xx (xx.x)	xx (xx.x)	xx (xx.x)
Race n(%)	<All categories on source>	xx (xx.x)	xx (xx.x)	xx (xx.x)
Sex n(%)	Male	xx (xx.x)	xx (xx.x)	xx (xx.x)
	Female	xx (xx.x)	xx (xx.x)	xx (xx.x)
Height (cm)
Weight (kg)
BMI (kg/m^2)

Note: Investigational Medicinal Product is delafloxacin, POS = powder for oral suspension, Regimen B, C and D with orange flavour
Regimen Key: A = 450 mg tablet (reference) fasted, B = 450 mg POS fasted, C = xxx mg POS <status>, D = xxx mg POS <status>

PROGRAM PATH: X:\~\QSCXXXXXX\~\TFLS\PRODUCTION\TAB-XX DDMMYY YYYY HH:MM

Programming note: This table will continue for all categories of ethnicity and race
Height, Weight and BMI will be assessed using the same descriptive statistics as Age
If any values are missing, then a "missing" row will be included in the table, as applicable

Sponsor/Quotient Sciences Confidential

Melinta Therapeutics
Protocol: ML-DEL-101-3727-1

Page x of y

TABLE 14.1.4
Lifestyle Details: Smoking History and Alcohol Consumption
Summary Statistics: Safety Population

		Sequence		
		ABC<D> (N=X)	BAC<D> (N=X)	Overall (N=X)
Does the subject smoke? (1)	NO PREVIOUSLY	xx (xx.x) xx (xx.x)	xx (xx.x) xx (xx.x)	xx (xx.x) xx (xx.x)
Alcohol Consumption (2)	NONE YES: NOT REGULARLY	xx (xx.x) xx (xx.x)	xx (xx.x) xx (xx.x)	xx (xx.x) xx (xx.x)

Note: Investigational Medicinal Product is delafloxacin, POS = powder for oral suspension, Regimen B, C and D with orange flavour
Regimen Key: A = 450 mg tablet (reference) fasted, B = 450 mg POS fasted, C = xxx mg POS <status>, D = xxx mg POS <status>
(1) Smoked or used e-cigarettes or nicotine replacement products in the last 12 months
(2) Excessive alcohol consumption (>21 units/week in males and >14 units/week in females)
1 unit = 1/2 pint beer, 25 mL of 40% spirit, 1.5 to 2 units = 125 mL glass of wine depending on type

PROGRAM PATH: X:\~\QSCXXXXXX\~\TFLS\PRODUCTION\TAB-XX

DDMMYYYY HH:MM

Sponsor/Quotient Sciences Confidential

Melinta Therapeutics
Protocol: ML-DEL-101-3727-1

Page x of y

TABLE 14.1.5
Extent of Exposure
Summary Statistics: Safety Analysis Set

Regimen	Subjects Dosed
	(N=X)
	n (%)
450 MG TAB FASTED	xx (xx.x)
450 MG POS FASTED	xx (xx.x)
XXX MG POS <STATUS>	xx (xx.x)
XXX MG POS <STATUS>	xx (xx.x)

Note: Investigational Medicinal Product is delafloxacin, POS = powder for oral suspension, Regimen B, C and D with orange flavour
Regimen Key: A = 450 mg tablet (reference) fasted, B = 450 mg POS fasted, C = xxx mg POS <status>, D = xxx mg POS <status>

PROGRAM PATH: X:\~\QSCXXXXXX\~\TFLS\PRODUCTION\TAB-XX

DDMMYYYY HH:MM

Sponsor/Quotient Sciences Confidential

Melinta Therapeutics
Protocol: ML-DEL-101-3727-1

Page x of y

TABLE 14.2.1
Plasma Pharmacokinetic Concentrations: Delafloxacin <(units)>
Summary Statistics: <PK Analysis Set/PK Analysis Subset>

Regimen	Time Point	Arithmetic (1)							Geometric (2)			
		n	n#	Mean	SD	CV%	Median	Min	Max	Mean	SD	CV%
450 MG TAB FASTED (N=X)	PRE-DOSE	xx	xx	xx.xx	xx.xx	xx.x	xx.xx	xx.x	xx.x	NC	NC	NC
	TIME POINT 1	xx	xx	xx.xx	xx.xx	xx.x	xx.xx	xx.x	xx.xx	xx.xx	xx.xx	xx.x
	TIME POINT 2	xx	xx	xx.xx	xx.xx	xx.x	xx.xx	xx.x	xx.xx	xx.xx	xx.xx	xx.x
	TIME POINT 3	xx	xx	xx.xx	xx.xx	xx.x	xx.xx	xx.x	xx.xx	xx.xx	xx.xx	xx.x

	<All other time points>	xx	xx	xx.xx	xx.xx	xx.x	xx.xx	xx.x	xx.xx	xx.xx	xx.xx	xx.x
450 MG POS FASTED (N=X)	PRE-DOSE	xx	xx	xx.xx	xx.xx	xx.x	xx.xx	xx.x	xx.x	NC	NC	NC
	TIME POINT 1	xx	xx	xx.xx	xx.xx	xx.x	xx.xx	xx.x	xx.xx	xx.xx	xx.xx	xx.x
	TIME POINT 2	xx	xx	xx.xx	xx.xx	xx.x	xx.xx	xx.x	xx.xx	xx.xx	xx.xx	xx.x
	TIME POINT 3	xx	xx	xx.xx	xx.xx	xx.x	xx.xx	xx.x	xx.xx	xx.xx	xx.xx	xx.x

	<All other time points>	xx	xx	xx.xx	xx.xx	xx.x	xx.xx	xx.x	xx.xx	xx.xx	xx.xx	xx.x
...

Note: Investigational Medicinal Product is delafloxacin, POS = powder for oral suspension, Regimen B, C and D with orange flavour
Regimen Key: A = 450 mg tablet (reference) fasted, B = 450 mg POS fasted, C = xxx mg POS <status>, D = xxx mg POS <status>
n# indicates the number of subjects with a BLQ value recorded at the time point indicated
(1) For arithmetic summary statistics, concentration values reported as BLQ have been set to zero
(2) For calculation of geometric summary statistics, values reported as BLQ have been set to $\frac{1}{2} \times$ LLOQ, except for pre-dose values which will not be summarised. The LLOQ value was <value, units>

PROGRAM PATH: X:\~\QSCXXXXXX\~\TFLS\PRODUCTION\TAB-XX

DDMMYYYY HH:MM

Programming note: This table will be continued for all time points
Programming note: This table will be continued for all regimens

Sponsor/Quotient Sciences Confidential

Melinta Therapeutics
Protocol: ML-DEL-101-3727-1

Page x of y

TABLE 14.2.2
Plasma Pharmacokinetic Parameters: Delafloxacin
Summary Statistics: <PK Analysis Set/PK Analysis Subset>

Regimen	Statistic	Parameter 1 (units)	Parameter 2 (units)	Parameter 3 (units)	All Other PK Parameters (units)
450 MG TAB FASTED (N=X)	n	xx	xx	xx	xx
	Mean	xx.xx	xx.xx	xx.xx	xx.xx
	SD	xx.xx	xx.xx	xx.xx	xx.xx
	CV%	xx.x	xx.x	xx.x	xx.x
	Median	xx.xx	xx.xx	xx.xx	xx.xx
	Min	xx.x	xx.x	xx.x	xx.x
	Max	xx.x	xx.x	xx.x	xx.x
	Geometric Mean	xx.xx	xx.xx	xx.xx	xx.xx
	Geometric SD	xx.xx	xx.xx	xx.xx	xx.xx
	Geometric CV%	xx.x	xx.x	xx.x	xx.x
450 MG POS FASTED (N=X)
...

Note: Investigational Medicinal Product is delafloxacin, POS = powder for oral suspension, Regimen B, C and D with orange flavour
Regimen Key: A = 450 mg tablet (reference) fasted, B = 450 mg POS fasted, C = xxx mg POS <status>, D = xxx mg POS <status>
For concentration parameters, BLQ values will be set to 0 for arithmetic statistics and to $\frac{1}{2} \times$ LLOQ for geometric statistics
The LLOQ value was <value, units>

PROGRAM PATH: X:\~\QSCXXXXXX\~\TFLS\PRODUCTION\TAB-XX

DDMMYYYY HH:MM

Programming note: This table will be continued for all time points

Sponsor/Quotient Sciences Confidential

Melinta Therapeutics
Protocol: ML-DEL-101-3727-1

Page x of y

TABLE 14.2.3.1
Plasma Pharmacokinetic Parameters: Delafloxacin
Statistical Analysis Results - Assessment of Relative Bioavailability: <PK Analysis Set/PK Analysis Subset>

Parameter	450 MG POS FASTED (N=XX)		450 MG TAB FASTED (N=XX)		Ratio (%) (2)	90% CI (3)
	n	Adj Geo Mean (1)	n	Adj Geo Mean (1)		
Cmax (units)	xx	xx.xx	xx	xx.xx	xx.xx	(xx.xx, xx.xx)
AUC(0-last) (units)	xx	xx.xx	xx	xx.xx	xx.xx	(xx.xx, xx.xx)
AUC(0-inf) (units)	xx	xx.xx	xx	xx.xx	xx.xx	(xx.xx, xx.xx)

Note: Investigational Medicinal Product is delafloxacin, POS = powder for oral suspension, Regimen B, C and D with orange flavour
Regimen Key: A = 450 mg tablet (reference) fasted, B = 450 mg POS fasted, C = xxx mg POS <status>, D = xxx mg POS <status>
Results obtained from mixed effects model of natural log transformed PK parameters including terms for regimen,
period and sequence fitted as fixed effects and subject nested within sequence fitted as a random effect
(1) Adj geo mean = adjusted geometric mean from model (2) Ratio of adj geo means with comparison presented
as test/reference (3) CI = confidence interval for ratio of adj geo means

PROGRAM PATH: X:\~\QSCXXXXXX\~\TFLS\PRODUCTION\TAB-XX

DDMMYYYY HH:MM

Sponsor/Quotient Sciences Confidential

Melinta Therapeutics
Protocol: ML-DEL-101-3727-1

Page x of y

TABLE 14.2.3.2
Plasma Pharmacokinetic Parameters: Delafloxacin
Statistical Analysis Results - Fixed Effects for Assessment of Relative Bioavailability: <PK Analysis Set/PK Analysis Subset>

Parameter	Effect (1)	df (2)	F-Statistic (3)	p-value (4)
Cmax (units)	REGIMEN	xx,xx	x.xx	0.xxx
	PERIOD	xx,xx	x.xx	0.xxx
	SEQUENCE	xx,xx	x.xx	0.xxx
AUC(0-last) (units)	REGIMEN	xx,xx	x.xx	0.xxx
	PERIOD	xx,xx	x.xx	0.xxx
	SEQUENCE	xx,xx	x.xx	0.xxx
AUC(0-inf) (units)	REGIMEN	xx,xx	x.xx	0.xxx
	PERIOD	xx,xx	x.xx	0.xxx
	SEQUENCE	xx,xx	x.xx	0.xxx

Note: Investigational Medicinal Product is delafloxacin, POS = powder for oral suspension, Regimen B, C and D with orange flavour
Regimen Key: A = 450 mg tablet (reference) fasted, B = 450 mg POS fasted, C = xxx mg POS <status>, D = xxx mg POS <status>
Results obtained from mixed effects model of natural log transformed PK parameters including terms for regimen,
period and sequence fitted as fixed effects and subject nested within sequence fitted as a random effect
(1) Fixed effects from the model (2) degrees of freedom for the fixed effects (3) F-statistic from the model for the
relevant fixed effect (4) p-value for the relevant fixed effect

PROGRAM PATH: X:\~\QSCXXXXXX\~\TFLS\PRODUCTION\TAB-XX

DDMMYYYY HH:MM

Sponsor/Quotient Sciences Confidential

Melinta Therapeutics
Protocol: ML-DEL-101-3727-1

Page x of y

TABLE 14.2.3.3
Plasma Pharmacokinetic Parameters: Delafloxacin
Statistical Analysis Results - Assessment of Food Effect: <PK Analysis Set/PK Analysis Subset>

Parameter	XXX MG POS <STATUS> (N=XX)		XXX MG POS <STATUS> (N=XX)		Ratio (%) (2)	90% CI (3)
	n	Adj Geo Mean (1)	n	Adj Geo Mean (1)		
Cmax (units)	xx	xx.xx	xx	xx.xx	xx.xx	(xx.xx, xx.xx)
AUC(0-last) (units)	xx	xx.xx	xx	xx.xx	xx.xx	(xx.xx, xx.xx)
AUC(0-inf) (units)	xx	xx.xx	xx	xx.xx	xx.xx	(xx.xx, xx.xx)

Note: Investigational Medicinal Product is delafloxacin, POS = powder for oral suspension, Regimen B, C and D with orange flavour
Regimen Key: A = 450 mg tablet (reference) fasted, B = 450 mg POS fasted, C = xxx mg POS <status>, D = xxx mg POS <status>
Results obtained from mixed effects model of natural log transformed PK parameters including terms for regimen,
period and sequence fitted as fixed effects and subject nested within sequence fitted as a random effect
(1) Fixed effects from the model (2) degrees of freedom for the fixed effects (3) F-statistic from the model for the
relevant fixed effect (4) p-value for the relevant fixed effect

PROGRAM PATH: X:\~\QSCXXXXXX\~\TFLS\PRODUCTION\TAB-XX

DDMMYYYY HH:MM

Programming note: a similar table will be produced for assessment of dose proportionality on dose corrected pk parameters if applicable,
i.e. Table [14.2.3.4]

Sponsor/Quotient Sciences Confidential

Melinta Therapeutics
Protocol: ML-DEL-101-3727-1

Page x of y

TABLE 14.2.4
Taste/Palatability Assessments
Taste/Palatability Analysis Set

<Overall Acceptability/Taste Attribute>

Statistic	450 MG POS FASTED(N=XX)	XXX MG POS <STATUS> (N=XX)	XXX MG POS <STATUS> (N=XX)
n	xx	xx	xx
Mean	xx.x	xx.x	xx.x
SD	xx.x	xx.x	xx.x
Median	xx.x	xx.x	xx.x
Min	xx.x	xx.x	xx.x
Max	xx.x	xx.x	xx.x
GRADE 1 n (%)	xx (xx.x)	xx (xx.x)	xx (xx.x)
GRADE 2 n (%)	xx (xx.x)	xx (xx.x)	xx (xx.x)
GRADE 3 n (%)	xx (xx.x)	xx (xx.x)	xx (xx.x)
GRADE 4 n (%)	xx (xx.x)	xx (xx.x)	xx (xx.x)
GRADE 5 n (%)	xx (xx.x)	xx (xx.x)	xx (xx.x)
GRADE 6 n (%)	xx (xx.x)	xx (xx.x)	xx (xx.x)
GRADE 7 n (%)	xx (xx.x)	xx (xx.x)	xx (xx.x)
GRADE 8 n (%)	xx (xx.x)	xx (xx.x)	xx (xx.x)
GRADE 9 n (%)	xx (xx.x)	xx (xx.x)	xx (xx.x)

Note: Investigational Medicinal Product is delafloxacin, POS = powder for oral suspension, Regimen B, C and D with orange flavour

